The treatment period has been extended from 4 weeks to 12 weeks. The extended treatment period includes 2 new visits; an 8-week Visit (Visit 4b) and a 12-week visit (Visit 4c). With the intention of further development of AZD5718 as a chronic treatment for the secondary prevention in high-risk CV patients, the aim is to evaluate the effects of inhibition of the 5-LO pathway mediated inflammation as well as physiological consequence and safety profile in a longer term, i.e. reasonably beyond the initial short-time treatment period of 4 weeks.

Therefore, treatment prolonged up to 12 weeks will allow to achieve and to assess sustained inhibition of leukotriene-mediated inflammation (urine-LTE₄ and blood-LTB₄) following the initial decrease after 4 weeks treatment. In addition, treatment with AZD5718 prolonged up to 12 weeks will allow to assess sustained dynamics, gradual and steady improvement of myocardial microvascular function (coronary flow reserve and echocardiography parameters) in post-ACS patients on top of the long-term Standard of Care. Extended up to 12 weeks treatment period will provide with more complete AZD5718 safety and tolerability profile with longer treatment exposure, on top of long-term Standard of Care in post ACS patients with CAD and support further clinical development.

Since some patients have already been randomized to the study, they will have a treatment period of 4 weeks, while future randomized patients will have a treatment period of 12 weeks.

The main endpoint, u-LTE₄, remains the same. Two new secondary endpoints are added: u-LTE₄ at 12 weeks and CFVR at 12 weeks.

The following sections of the clinical study protocol (CSP) have been updated to reflect this change: Section 1.2 (Rationale for study design, doses and control groups), Section 1.3 (Benefit/risk and ethical assessment), Section 1.4 (Study Design including Figure 1), Section 2 (Study objectives) and Section 4.1 (Study Procedures including Table 1), Section 7.2 (Dose and treatment regimens) and Section 8 (statistical analyses). All text in the CSP mentioning the duration of the study have been updated accordingly, including the Study Title.

Increase in number of patients

The total number of patients that will be randomized in the study has been increased from 100 to approximately 138. The reason for increasing the total number of patients is to make sure that there are enough patients to evaluate the sustained effect on CFVR after 12 weeks, that is, about 33 evaluable patients per arm for AZD5718 [REDACTED] and placebo. An evaluable patient is defined as a patient with a valid CFVR measurement at Visit 2 (baseline), and one postbaseline visit as judged by the CFVR Core lab. The total number of patients for evaluation of uLTE₄ and CFVR at week 4 will be more than 33 patients per high-dose and

placebo arm (exact number will be known at the unblinding at the end of the trial). This is due to the fact that patients that are already randomized to the study (approximately 38) will have a treatment period of 4 weeks while future randomized patients (approximately 100) will have a treatment period of 12 weeks.

Section 1.4 (Study Design) has been updated to reflect this change, however, the updated numbers are reflected in all relevant sections of the CSP.

Interim analysis

The interim analysis is updated as follows: The text is revised to alter the futility interim analysis to two administrative interim analyses for internal decision making. The futility analysis has been removed to be able to evaluate the sustained effect on u-LTE₄ at 12 weeks. The focus of the study extended to 12 weeks aiming on evaluation 5-LO pathway inhibition, ie not only at the end of 4 weeks but at the end of 12 weeks to ensure the use of the drug in a chronic setting. The futility analysis has therefore been changed into two administrative interim analyses for internal decision making. In the event of positive outcome at any of the administrative interim analyses an evaluation of exposure-response relationship may be performed. This is reflected in the Study Synopsis (Statistical methods) and Section 8.5.6 (Interim analysis).

Biomarker sampling

An additional biomarker sample will be collected at day 2 after the ACS.

The rationale for adding a day 2 sample is to be able to model the kinetics of inflammatory biomarkers post ACS. A minimum of three samples from each patient (ideally before and after the peak expression) is required for mathematical modelling. Individual differences between the patients are expected. Therefore, several samples from the same patient are required. Since, the peak expression is expected to take place at around day 1-3 post ACS, namely this timeframe is the most crucial for the biomarker kinetics and therefore a day 2 sample has been added.

The following sections have been updated to reflect this change: Section 1.4 (Study Design) and Section 4.1 (Study Procedures Visit 1 as well as Table 1).

Safety sampling

TSH, free T3, free T4 and total T4 has been added to the safety laboratory assessments at Visit 2 (Baseline at Randomization), Visit 4 (4 weeks), Visit 4c (12 weeks) and Visit 5 (Follow-up). This decision is based on a recently completed 3 months toxicity study in rats. In rats, though not in dogs, treatment with AZD5718 in doses of QD 1000 mg/kg/day (> 200 folds higher than clinical exposure) caused minimal follicular cell hypertrophy in the thyroid gland which is considered as adaptive rather than adverse and based upon experience, most likely reversible. This risk is not anticipated in humans, however repeated safety assessment of thyroid functions will be performed in study subjects.

This is reflected in the List of abbreviations and definition of terms, Section 1.3

(Benefit/risk and ethical assessment), Section 4.1(Study Procedures including Table 1) and Section 5.2.1(Laboratory safety assessments including Table 2).

Non-substantial amendments to the protocol:

Section 5.3.1(Other research biomarker assessments): ApoB will be analysed instead of ApoB100. The reason behind the change is that local labs do not have the possibility to analyse ApoB100, as originally planned, only ApoB. The change applies to all sections mentioning ApoB100.

Section 6.4 (Reporting of serious adverse events): The text was revised to say that “If the WBDC system is not available, then the Investigator or other study site staff reports a SAE to the appropriate AstraZeneca representative by fax ([contact]) or E-mail “[contact]” instead of by phone as originally stated. This was revised based on a study team decision in order to be in line with normal reporting routines.

Section 8.3.2 (Safety analysis set): “Major deviation” has been replaced by “important protocol deviation”.

Section 8.4.1 (Efficacy variables):

Corrected text to state that LV Global Circumferential Strain (GCS) is only to be recorded at rest and not at hyperaemia.

In addition, minor edits in terms of spelling, lay-out and clarifications have been made throughout the document.

Version: 2.0 dated 10 January 2018

Changes to the protocol are summarized below

Section 2.4 (Exploratory objectives): the exploratory objective related to gyrocardiography was removed, based on a decision by the project team. Consequently, all text in the CSP where gyrocardiography measurement is described was removed: Section 4.1 (Visits 2, 4 and 5 and Table 1), Section 5.1.5 and Section 8.4.3.

Section 3.2 (Exclusion criteria):

Criterion no 13 was updated as follows:

“NYHA class III-IV heart failure **or decompensated heart failure** at discharge or hospitalization for exacerbation of chronic heart failure within the previous 3 months from

ACS “

This was added based on a request by the Swedish MPA.

Criterion no 16 was updated as follows:

“Known allergy to adenosine **and mannitol, or experience of previous adverse effects of adenosine stress testing.**”

This was added based on a request by the Swedish MPA.

Criterion no 26 was clarified as follows:

“Participation in another **interventional** clinical study with an investigational **pharmaceutical** product during the last 3 months **also including drug eluting stents**

This was clarified based on a project team decision.

Section 3.4 ([Procedures for handling incorrectly enrolled or randomized patients](#)): The section was revised to say that when a patient does not meet all the eligibility criteria but is randomized in error or incorrectly started on treatment, the patient must discontinue the treatment and be withdrawn from the study.

The revision is based on a request from the Swedish MPA.

Section 4.1 ([Study Procedures](#)):

Corrected text for Visit 2 by removing incorrect text about CFVR measurement at screening (inconsistent with Table 1).

Corrected text for Visit 5 by removing incorrect text about PRO questionnaire (inconsistent with Table 1).

Section 8.4.4([Exploratory biomarkers](#)): Removed GDF15, IL-1B and IL-6 from the list of exploratory biomarkers to be summarized statistically in the CSR, instead they will be referred to in an exploratory SAP and reported separately. This is based on a decision by the project team.

Version: 1.0 dated 5 July 2017

Initial creation

This Clinical Study Protocol has been subject to a peer review according to AstraZeneca Standard procedures. The Clinical Study Protocol is publicly registered and the results are disclosed and/or published according to the AstraZeneca Global Policy on Bioethics and in compliance with prevailing laws and regulations

CLINICAL STUDY PROTOCOL SYNOPSIS

A 12-week, randomized, single-blind, placebo-controlled, multi-centre, parallel group, phase IIa study to evaluate efficacy, safety and tolerability of oral AZD5718 after 4- and 12-weeks of treatment in patients with coronary artery disease (CAD)

International Co-ordinating Investigator:

[REDACTED]

Study site(s) and number of subjects planned

This study will be a multi-centre study conducted at approximately 10 centres in 3 countries. Approximately one hundred and thirty-eight (138 patients with coronary artery disease (CAD) will be randomized to ensure at least 66 evaluable patients receiving 12 weeks treatment with AZD5718 [REDACTED] or placebo. About 20% of the randomized patients will receive AZD5718 [REDACTED]. The patients on lower dose are included to guide dose selection in future studies. The study was originally designed to be a 4-week study and was amended to be a 12-week study. Therefore, the total number of patients is greater than required for a 12 weeks study (about 100), this since some patients will only have 4 weeks of treatment.

Study period

Estimated date of first patient enrolled Q4 2017

Estimated date of last patient completed Q1 2020

Phase of development:

Phase IIa

Study design

Randomized, single-blind, placebo-controlled, parallel-group, multicentre study in patients with CAD.

NB. The study was originally designed to be a 4-week study and was amended to be a 12-week study. As a consequence, some patients will have a treatment period of 4 weeks only while others will have a treatment period of 12 weeks.

Objectives

Primary Objective:	Outcome Measure:
To assess the pharmacodynamic (PD) effect of AZD5718 by assessment of urine-leukotriene E4 (u-LTE ₄) at 4 weeks in CAD patients.	Percentage change from baseline in levels of u-LTE ₄ (see Section 8.4.1)

Secondary Objectives:	Outcome Measures:

 To assess the pharmacodynamics (PD) effect of AZD5718 by assessment of urine-leukotriene E4 (u-LTE₄) at 12 weeks in CAD patients. 	Percentage change from baseline in levels of u-LTE ₄ (see Section 8.4.1)

 To assess the effect of AZD5718 on change from baseline in Coronary Flow Velocity Reserve (CFVR) at 12 weeks in CAD patients. 	Change from baseline in Coronary Flow Velocity Reserve (CFVR) in the mid-distal segment of the left anterior descending (LAD) coronary artery under adenosine infusion measured by Transthoracic Doppler Echocardiography (TDE)

 To assess the effect of AZD5718 on change from baseline in Coronary Flow Velocity Reserve (CFVR) at 4 weeks in CAD patients. 	Change from baseline in Coronary Flow Velocity Reserve (CFVR) in the mid-distal segment of the left anterior descending (LAD) coronary artery under adenosine infusion measured by Transthoracic Doppler Echocardiography (TDE)

 To assess the pharmacokinetics (PK) of AZD5718 after repeated oral dosing at 4 and 12 weeks in CAD patients 	Standard model population pharmacokinetic (PK) parameters to be reported in a separate report.

 To assess the effect of AZD5718 on coronary flow parameters at 4 weeks in CAD patients 	Change from baseline in: 
 - LAD resting mean diastolic flow velocity - LAD hyperaemic flow velocity

 To assess the effect of AZD5718 on change in echocardiographic parameters at 4 weeks in CAD patients. 	Change from baseline in: 
 - Left Ventricular (LV) Ejection Fraction (LVEF) - LV global longitudinal strain (GLS) - LV global circumferential strain (GCS) - LV longitudinal early diastolic strain rate

Exploratory Objective:	Outcome Measures:

 To assess the effect of AZD5718 on coronary flow parameters at 12 weeks in CAD patients 	Change from baseline in: 
 LAD resting mean diastolic flow velocity LAD hyperaemic flow velocity

 To assess the effect of AZD5718 on change in echocardiographic parameters at 12 weeks in CAD patients. 	Change from baseline in: 
 Left Ventricular (LV) Ejection Fraction (LVEF) LV global longitudinal strain (GLS) LV global circumferential strain (GCS) LV longitudinal early diastolic strain rate

Safety Objective:	Outcome Measures:
To assess the safety and tolerability of AZD5718 in CAD patients	
 Adverse Events/Serious Adverse Events (AEs/SAEs) Vital signs Collection of clinical chemistry/haematology parameters Electrocardiogram (ECG) assessments

Target subject population

Male and female CAD patients aged 18-75, with BMI 18- 35 kg/m² who are found eligible for the study after review of the inclusion and exclusion criteria and who have signed Informed Consent Form (ICF).

Duration of treatment

Eligible patients will be randomized in a ratio 2:1:2 to receive either AZD5718 (), AZD5718 or Placebo. Treatment duration will be 12 weeks, once daily administration, to be taken with approximately 200 ml water in the morning with no restrictions on food intake.

Investigational product, dosage and mode of administration

Investigational product	Dosage form and strength	Dose	Manufacturer
AZD5718	of AZD5718 tablet		AstraZeneca
AZD5718	of AZD5718 tablet		AstraZeneca

Investigational product	Dosage form and strength	Dose	Manufacturer
Placebo to match (PTM) AZD5718 [REDACTED]	PTM AZD5718 [REDACTED] [REDACTED] tablet	[REDACTED]	AstraZeneca
Placebo to match (PTM) AZD5718 [REDACTED]	PTM AZD5718 [REDACTED] tablet	[REDACTED]	AstraZeneca

Statistical methods

The primary efficacy and the first secondary variable will each test the null hypothesis that patients given AZD5718 [REDACTED] have less than 80% inhibition of u-LTE₄ compared to placebo, versus the alternative hypothesis that patients given AZD5718 [REDACTED] have equal or more than 80% inhibition of u-LTE₄ compared to placebo (one-sided 95% confidence interval).

The second and third secondary efficacy variable measuring change from baseline in CFVR will test the null hypothesis of no increase in CFVR in patients given AZD5718 [REDACTED] compared to placebo, versus the alternative hypothesis of an increase in CFVR in patients given AZD5718 [REDACTED] compared to placebo (one-sided 95% confidence interval).

The primary efficacy variable and the three first secondary efficacy variables measuring will be analysed using a repeated measurement model with treatment, type of Myocardial Infarction (MI) (STEMI vs NSTEMI) as factors and baseline value as covariate, with spatial power covariance structures (generalisation of an auto regressive covariance structure allowing for none-equidistant time points).

Efficacy variables will be analysed using the intention to treat (ITT) population. The randomization will be stratified with type of MI as a factor ST-elevation MI vs non-ST-elevation MI (STEMI vs NSTEMI).

Given anticipated effect size, 40 randomized patients on AZD5718 [REDACTED] and 40 randomized patients on placebo is needed accounting for non-evaluable patients to achieve an overall power of approximately 80% for the primary endpoint and secondary endpoints analysing change in CFVR. For dose selection in future studies, a treatment arm with patients receiving AZD5718 [REDACTED] is included in the study.

Two administrative interim analyses will be conducted. The first one is planned after at least 45 patients have performed their CFVR measurement at Visit 4 and the second after at least 100 patients have performed their CFVR measurement at Visit 4.

TABLE OF CONTENTS	PAGE
TITLE PAGE.....	1
VERSION HISTORY	2
CLINICAL STUDY PROTOCOL SYNOPSIS	7
TABLE OF CONTENTS	11
1. INTRODUCTION	20
1.1 Background and rationale for conducting this study	20
1.2 Rationale for study design, doses and control groups.....	21
1.2.1 Dosing rationale	23
1.3 Benefit/risk and ethical assessment	23
1.4 Study Design.....	24
2. STUDY OBJECTIVES	27
2.1 Primary objective	27
2.2 Secondary objectives.....	27
2.3 Safety objectives	28
2.4 Exploratory objectives	28
3. PATIENT SELECTION, ENROLMENT, RANDOMIZATION, RESTRICTIONS, DISCONTINUATION AND WITHDRAWAL.....	29
3.1 Inclusion criteria	29
3.2 Exclusion criteria	29
3.3 Patient enrolment and randomization	31
3.4 Procedures for handling incorrectly enrolled or randomized patients	31
3.5 Methods for assigning treatment groups	32
3.6 Methods for ensuring blinding	32
3.7 Methods for unblinding.....	32
3.8 Restrictions	33
3.8.1 Medication restrictions.....	33
3.8.2 Dietary restrictions.....	33
3.8.3 Alcohol, Drugs of abuse, Tobacco and Caffeine Restrictions.....	33
3.8.4 Restrictions for male study subjects	33
3.8.5 Other Restrictions	34

3.9	Discontinuation of investigational product	34
3.9.1	Procedures for discontinuation of a subject from IP	34

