8.2 Sample size estimate

The study has been powered to show a statistically significant result for the primary endpoint, first, second and third secondary endpoints. To preserve the overall type1-error at 5% when testing these four endpoints a Hierarchical Procedures will be used (Dmitrienko A. et al 2006). This procedure implies that one will test the four endpoints in a predefined sequence: test of main objective, test of first secondary objective, test of second secondary objective, test of third secondary objective. The test procedure will stop as soon as the first none-significant test, one-sided test at a 5% level, occur and all following test will be declared as none-significant.

The Hierarchical testing sequence for the four endpoints are:

1. u-LTE₄ at 4 weeks
2. u-LTE₄ at 12 weeks
3. CFVR at 12 weeks
4. CFVR at 4 weeks

Data from MAD study shows inhibition of u-LTE₄ by AZD5718 [REDACTED] can be assumed to be log-normally distributed, with an expected inhibition of u-LTE₄ of approximately 96% and a standard deviation of <4%. Patients given placebo are expected to have no inhibition of u-LTE₄ with the same standard deviation (on the logarithmic scale) as patients given AZD5718 [REDACTED]. Given this, 33 evaluable patients in the AZD5718 [REDACTED] group and 33 evaluable patients given placebo will be sufficient to achieve > 99% power to show a statistically significant inhibition of u-LTE₄ of at least 80%, using a one-sided confidence interval of 95% at week 12.

Assuming a log-normal distribution of the CFVR and an expected 20% increase in CFVR in the AZD5718 [REDACTED] group compared to placebo with a coefficient of variation (CV) of 30%, 33 evaluable patients per arm is required to achieve 80% power with a one-sided confidence interval of 95%.

About 40 randomized patients per arm (AZD5718 [REDACTED] or placebo) treated for 12 weeks is needed to account for non-evaluable patients (approximate 18% dropout).

For supporting dose selection in future studies, a treatment arm with about 20 randomized patients receiving AZD5718 [REDACTED] for 12 weeks is included in the study, in order to get 17 evaluable patients. This number of subjects, 17, patients has been deemed to provide sufficient exposure-response information.

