8.5.1 Analysis of the primary variable(s)

The primary efficacy variable will test the null hypothesis that patients given AZD5718 [REDACTED] have less than 80% inhibition of u-LTE₄ compared to placebo, versus the alternative hypothesis that patients given AZD5718 have equal or more than 80% inhibition of u-LTE₄ compared to placebo (one-sided confidence interval) at week 4.

The primary efficacy variable will be analysed as change from baseline using a repeated measures model with type of MI (STEMI vs NSTEMI), time from randomization (days), treatment and time treatment interaction as fixed effects with baseline value as covariate. The covariance structure will be spatial power law covariance structures (generalisation of an auto regressive covariance structure allowing for none equidistant time points). All available data from each patient will be used for the analysis. The analysis will be done on loge scale. However, the result will be back transformed to original scale.

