8.5.2 Analysis of the secondary variables

The first secondary, second secondary and third secondary efficacy variable will be analysed in the same type of model as for the primary endpoint, that is, a repeated measurement model with the same structure as described for the primary variable. All three endpoints will be measured as change from baseline and the analyses will be done on logarithmic transformed data. However, the result will be back transformed to original scale.

The models for analysis of all other secondary variables will be defined in the SAP. In general, an analysis of covariance or as a repeated measurement model will be used. The SAP will also describe which variable that will be analysed on original scale or on log scale. All results from transformed variables will be back transformed to the original scale.

If data permits a population PK model will be developed, possibly with the support of PK data from studies D7550C00001 and D7550C00002, using nonlinear mixed effects regression

analysis in NONMEM. Furthermore, if data allows, the population PK model may be coupled with separate PD models for u-LTE₄ and for CFVR.

All PK/PD modelling will be described in a separate data analysis plan. Moreover, the results of any such modelling will be provided in a separate population PK/PD report (as an appendix to the CSR or as a stand-alone report).

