8.6.2 Analysis of secondary efficacy variables

Change from baseline in CFVR

The second secondary efficacy endpoint is the change from baseline in CFVR at Visit 4c.

The null hypothesis of no increase in CFVR in subjects given AZD5718 compared to placebo will be tested.

The third secondary efficacy endpoint is the change from baseline in CFVR at Visit 4.

The null hypothesis of no increase in CFVR in subjects given AZD5718 compared to placebo will be tested.

All the analyses will be performed based on the Efficacy Analysis Set. All the assessments related to the secondary variables are described in section 6.4.2.

Both the second and third secondary endpoints will be analysed using the Mixed Model Repeated Measures (MMRM) described in section 7.1 using data from visit 2, 4 and 4c.

CFVR is log-Normal distributed. The analysed change from Baseline is calculated as Visit value in log minus the Baseline value in log.

One-sided test will be used to compare the change from baseline observed in the active group, vs the change from baseline observed in the placebo group. Alpha level will be set at 0.05. The reportable results will be those for log-Normal variables.

Comparison of AZD5718 versus placebo will also be assessed within the same model.

For further details on the statistical model please refer to the Appendix 2 and to the table in Appendix 3.

In addition to the results above, the following will also be generated:

- Descriptive statistics by group for all visits, for the actual value and for the change from baseline. Change from baseline is calculated as Visit value minus Baseline value;
- Graphical representations of change from baseline (mean(SD)) over time and by groups;
- Forest plots based on the results of the two models.

CFVR will be also listed for Efficacy Analysis Set at each visit.

A sensitivity analysis may be performed as detailed in section 7.2.

Distribution:

Original:

Copy:

TPCA025 Version 2 (based on TPQA036 Version 2) Effective Date: 27th August 2017 Prior Effective Date: 21st December 2016

Sponsor:	AstraZeneca AB	Protocol/CIP Number:	D7550C00003
CIL Project Number:	40343		

Other secondary variables

The other secondary endpoints related to all other secondary variables are the changes from baseline at Visit 4. The exploratory endpoints related to all other secondary variables are the changes from baseline at Visit 4c.

The other secondary variables are:

- LAD resting mean diastolic flow velocity

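### Does the synopsis overstate power by calling about 80% the overall power for the primary and CFVR endpoints?

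*Protocol*

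**What the plan says.** The synopsis (Statistical methods) puts one figure on several endpoints. Forty randomized patients on the higher-priority AZD5718 arm and 40 on placebo are said "to achieve an overall power of approximately 80% for the primary endpoint and secondary endpoints analysing change in CFVR". The plural covers CFVR at week 12 and at week 4, the second and third secondary endpoints.

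Protocol 8.2, repeated in SAP 4.5, sets out a fixed sequence, each step one-sided at 5%: u-LTE4 at week 4, u-LTE4 at week 12, CFVR at week 12, CFVR at week 4. It opens by saying that the study is powered for all four. It then gives two separate calculations at 33 evaluable patients per arm. For u-LTE4 this number "will be sufficient to achieve > 99% power to show a statistically significant inhibition". For CFVR, with a 20% increase and a 30% CV, "33 evaluable patients per arm is required to achieve 80% power with a one-sided confidence interval of 95" per cent; no visit is named.

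The protocol version history links the 33 to week 12, the aim being "enough patients to evaluate the sustained effect on CFVR after 12 weeks, that is, about 33 evaluable patients per arm". It adds that the number available for u-LTE4 and "CFVR at week 4 will be more than 33 patients per high-dose" and placebo arm, because patients randomized before the amendment have 4 weeks of treatment only.

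The analysis model has "treatment and time treatment interaction as fixed effects with baseline value as covariate" (Protocol 8.5.1). CFVR uses "a repeated measurement model with the same structure as described for the primary variable" (Protocol 8.5.2). SAP 8.6.2 confirms one repeated-measures model for both CFVR visits.

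**The concern.** In a plan with a four-step fixed sequence, *overall power* reads naturally as the chance of passing all the named tests together. The 80% is the power of one CFVR comparison taken alone. If two CFVR tests must both succeed, the joint probability cannot exceed the smaller of the two powers, and it is lower unless the tests are strongly correlated. Neither document gives a joint power, a correlation between the CFVR visits, or a statement of whether the 30% CV is before or after baseline adjustment.

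A reader who relies on the synopsis could therefore believe that the trial has an 80% chance of succeeding on the primary and both CFVR endpoints, when nothing in the plan derives that. If the true joint figure were well below 80%, the synopsis would oversell the design.

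**Working it through.** **Single CFVR comparison (Protocol 8.2).** Inputs: ratio 1.20, CV 30%, one-sided alpha 0.05, 33 per arm.

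- delta = ln 1.2 = 0.1823; log-SD s = sqrt(ln(1 + 0.30²)) = 0.2936.
- n per arm = 2 [s (1.645 + 0.842) / delta]² = 32.1, so 33.
- SE = 0.2936 × sqrt(2/33) = 0.0723; noncentrality = 0.1823 / 0.0723 = 2.52; noncentral-t power = 80.3%.
- Dropout: 33 / 0.82 = 40.2, in line with about 40 randomized.

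The plan's figure reproduces, and it is the power of one comparison.

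**u-LTE4 (Protocol 8.2).** Inputs: 96% inhibition (residual ratio 0.04), SD at its stated upper bound of 0.04, threshold 80% (ratio 0.20).

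- CV of the residual = 0.04 / 0.04 = 100%; log-SD = sqrt(ln 2) = 0.833; delta = ln(0.20 / 0.04) = 1.609.
- SE = 0.833 × sqrt(2/33) = 0.205; noncentrality = 7.85; power above 99.99%.

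**Sequence through CFVR at week 12.** With u-LTE4 power about 1, this is 1 × 1 × 0.803, or about 80%. If each u-LTE4 test had only 99% power and the tests were independent, it would be 0.99² × 0.803 = 79%. The synopsis figure holds this far.

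**Adding CFVR at week 4.**

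*Patients at week 4.* About 38 patients had been randomized to 4 weeks of treatment. With 2:1:2 allocation, and assuming the 33/40 evaluable fraction also applies at week 4, this adds 38 × 0.4 × 33/40 = 12.5, taken as 12 per arm. That gives about 45 per arm at week 4 and 33 at week 12. Single-comparison power at 45 per arm is 89.9%.

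*Joint distribution.* Assume a 20% effect and the same SD at both visits, with between-visit correlation rho. Under the planned model, week-4 data from the 4-week patients also inform the week-12 estimate:

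- Var(week 12) = (2s²/33) × [1 − rho² (1 − 33/45)]
- Var(week 4) = 2s²/45
- Cov = rho × 2s²/45

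Joint power is the bivariate normal probability that both statistics exceed their one-sided 5% t critical values.

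| 30% CV read as | rho 0.3 | 0.5 | 0.7 | 0.9 |
|---|---|---|---|---|
| after baseline adjustment | 0.745 | 0.770 | 0.805 | 0.852 |
| before adjustment, baseline correlation 0.3 | 0.789 | 0.811 | 0.841 | 0.883 |
| before adjustment, baseline correlation 0.5 | 0.868 | 0.883 | 0.905 | 0.933 |

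In the second and third rows s is multiplied by sqrt(1 − r²), where r is the baseline correlation. The values of rho and r are assumptions.

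If the borrowing across visits is ignored (the bracket in Var(week 12) set to 1), the first row becomes 0.738, 0.749, 0.763 and 0.779. So the least favourable reading is a few points under 80%, and the other readings are near or above it.

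A calculation with 33 per arm at both visits would give lower figures, but the version history says the week-4 number exceeds 33 per arm, so that scenario does not describe this trial.

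**The case for a change.** The strongest case for acting is that the sentence names CFVR endpoints in the plural, so week 4 is inside the claim and has no calculation of its own. It also credits the 80% to 40 randomized patients per arm, whereas the support at week 4 comes from additional 4-week patients whose effect is never worked out. Many readers judge a trial from the synopsis, and deleting one word would cost nothing.

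The textual part of this stands: *overall* has no derivation, and the 80% is a single-comparison power. The step from there to a defect does not. The sentence omits u-LTE4 at week 12, the second step of the hierarchy, so it is not worded as the power of the full sequence. It can equally be read as saying that this size gives at least about 80% for each endpoint named. That is true under the stated assumptions: 80.3% for CFVR at week 12 and about 90% at week 4 with 45 per arm.

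The edit is also less clean than it looks. Protocol 8.2 and SAP 4.5 themselves say that the study is powered for all four endpoints. If the synopsis needed correcting, so would that sentence; if that sentence is acceptable as power per comparison, the synopsis is a mild paraphrase of it. Attaching the 33 firmly to week 12 would also claim more than 8.2 does. Protocol 1.4 defines an evaluable patient by a valid baseline and one postbaseline CFVR measurement, which could be the week-4 one.

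**Conclusion.** No change follows. This is loose wording in a summary, not an arithmetic error: every power and sample size stated in Protocol 8.2 and SAP 4.5 reproduces. Eighty per cent is right for one CFVR comparison and for the sequence through CFVR at week 12. For all four tests, joint power is about 74% to 93% under the planned model with about 45 per arm at week 4, and the documents' inputs do not place it above or below 80%. That range rests on an assumed between-visit correlation of 0.3 to 0.9, an assumed baseline correlation of 0.3 or 0.5 where the CV is read as unadjusted, and equal effects at both visits.

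The consequence is small even on the least favourable reading. CFVR at week 4 is the last step, so failing it leaves the week-12 result and both u-LTE4 results intact. A statistician who wants the power basis will find the two figures stated separately, with effect size, variability, alpha, sidedness and dropout, in the sections that govern the design. Rewording the synopsis would alter no test, alpha level, sample size or analysis.
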